### **11.2 Day 2 Post-operative (No Visit Required)**

Subjects begin taking Study Medication

### **11.3 Day 7-10 Post-operative (No Visit Required)**

Subjects visit their local laboratory and a Basic Metabolic Panel is drawn to include:

- Glucose;
- Calcium;
- Sodium;
- Potassium;
- Carbon Dioxide (CO2);
- Chloride;
- Blood Urea Nitrogen (BUN); and
- Creatinine.

In addition, each subject will be contacted by a Study Team member to confirm that the blood draw has occurred, and Study Medications are being logged. The occurrence of protocol deviations and all adverse events will be recorded.

### **11.4 Telephone Contact by Study Team Post-operative day 30- (No Visit Required) (approximately one month)**

Study Medication is expected to be completed at this time. A Study Team member will contact each subject to confirm that the Study Medication has been completed and logged. Subjects will be asked to send to the Study Team, a copy of the Study Medication Log. The occurrence of protocol deviations and all adverse events will be recorded.

### **11.5 Visit 2: Three Months Post-operative Clinic Visit (+/- 4 weeks)**

Subjects will be asked to complete the following questionnaires either on paper or in electronic format.

- SF-12 – Short Form General Health Survey;
- Patient Satisfaction;
- Harris Hip Score (HHS);
- Vail Hip Score (VHS);
- Hip Outcome Score (HOS);
- Western Ontario and McMaster Universities Osteoarthritis Index (WOMAC);

- Tegner Activity Scale; and
- VAS Pain - Visual Analogue Scale for Pain.

Subjects will receive a focused physical exam, review of all medications, strength testing and range of motion (ROM) assessment. Protocol deviations and adverse events related to the target hip will be recorded.

**11.6 6 Months Post-operative -(No Visit Required) (+/- 4 weeks)**

A Study Team member will contact each subject. Subjects will complete electronically each questionnaire as above. Adverse events related to the target hip and protocol deviations will be recorded.

**11.7 12 Months Post-operative -(No Visit Required) (+/- 8 weeks)**

A Study Team member will contact each subject. Subjects will complete electronically each questionnaire as above. Adverse events related to the target hip and protocol deviations will be recorded.

**11.8 Visit 3: 18 Months Post-operative (+/- 8 weeks)**

All procedures performed in Visit 3 will be repeated. In addition, subjects will undergo a Morphological and quantitative T2 MRI to be performed at Steadman Research Institute according to a specific and consistent imaging protocol. Adverse events related to the target hip and protocol deviations will be recorded.

**11.9 Unscheduled Visits and/or Subject Contact**

In the event that additional visit(s) or subject contact is required other than those described in the protocol, the information must be documented in the appropriate study document.

---

## **12.0 Study Management of Adverse Events**

### **12.1 Definition**

Adverse Event – An adverse event (AE) is any untoward medical occurrence in a subject administered a Study Medication and which does not necessarily have a causal relationship with this treatment. An AE can therefore be any unfavorable and unintended sign (including an abnormal laboratory finding), symptom, or disease temporally associated with the use of whether or not related to the Study Medication (ICH E2A II/A/1, 21 CFR 312.32).

All pre-existing medical conditions will be recorded on the medical history study document. Starting with the administration of the Study Medication any new experience that was not present at baseline or worsening of an event present at baseline in intensity or frequency, is considered an adverse event.

Note: Unchanged, chronic conditions are NOT adverse events and should not be recorded.

It is recognized that subjects will exhibit (throughout follow-up) symptoms of the underlying disease process of that fluctuates in severity and duration.

Adverse events will include those occurrences, which when compared to before treatment meets any of the following criteria:

- Represent a new event or escalation of an event;
- Require a new escalation in treatment;
- Lasts longer;
- Experienced more frequently;
- More intense;
- Different in character ( e.g. stabbing vs. ache);
- Experienced in a different part of the body; and/or
- Brought on by activity that previously did not cause the symptom.

### **12.2 Recording Adverse Events**

Adverse events that occur up to 35 days +/- 3 days after the beginning Study Medication administration will be recorded. Terms should be recorded consistently, using acceptable medical terms. When possible, a diagnosis should be identified as the AE (i.e., disease or syndrome) rather than the component signs and symptoms, and recorded on the case report form (e.g., record congestive heart failure rather than dyspnea, rales and cyanosis). However, signs and symptoms considered unrelated to encountered syndromes or diseases are to be

---

recorded as individual AEs (e.g., if congestive heart failure and severe headaches are observed at the same time, each experience is to be recorded as an individual AE). The AE should not be recorded as a procedure or clinical measurement (i.e., a laboratory or vital sign) but should reflect the reason for the procedure or diagnosis.

Death is considered to be an outcome of an AE. The cause of death (rather than the term “death”) should be recorded on the serious AE and death report case report forms.

Subjects should be encouraged to report AEs spontaneously or in response to general, non-directed questioning. At each required visit (or whenever reported) during the study, all AEs that have occurred since the previous visit must be recorded on the AE case report form.

All AEs, regardless of seriousness, severity, or presumed relationship to the treatment must be recorded using medical terminology

All AEs must be followed until resolution or until a stable clinical endpoint is reached. All measures required for AE management and the ultimate outcome of the AE must be recorded in the study document. All adverse events that occur in the study population will be tabulated and summarized.

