| Screening Tools:
(At preoperative visit) | 
Standard of Care Data Collected
 
Basic demographic data, medical and surgical history, medication review, age, gender, body mass index and chronicity of the injury, co-morbidities, smoking status, range of motion, strength and size of the cartilage lesion will be recorded. Circumduction evaluation exercises and range of motion restrictions will be evaluated. Patient Reported Outcomes (PRO) tools which will be repeated, at key study intervals will be performed and a T2 MRI of the hip will be performed as standard of care diagnosis.
  |
| Subject Follow-up:                          | 
All adverse events will be assessed during Study Medication administration and for 5 days (+/- 3) days after medication completion. After Study Medication administration only those adverse events related to the target hip will be collected. In addition, the following data will be collected:
 
Visit 1: Post Op Day 1:
 
Subject discharge for the hospital is anticipated to occur on POD1. At discharge the subject will be provided with a blood pressure cuff and be trained on “at home” blood pressure monitoring and recording. They will also be provided with a prescription for Study Medication which will be written in a blinded format for either losartan or placebo. Subjects will be instructed to visit the Vail Hospital Pharmacy to obtain the correct, blinded Study Medication. Study Medication Logs, and Blood Pressure Logs will be provided, with instructions for completion.
 
Subjects will be instructed to undergo post-operative physical therapy, and they will be provided with a document outlining recommended content. They will also be provided with a
 |

|  |   |
|--|---|

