|  | 
prescription for a basic metabolic panel to be drawn by their local laboratory within 7-10 days post medication initiation.
 
POD Day 2
Subjects begin taking Study Medication
 
POD Day 7-10 (No Visit Required)
Subjects visit their local laboratory and a Basic Metabolic Panel is drawn to include: Glucose, Calcium, Sodium, Potassium, Carbon Dioxide (CO2), Chloride; Blood Urea Nitrogen (BUN), and Creatinine.
 
In addition, each subject will be contacted by a Study Team member to confirm compliance, and Study Medications are being logged. All adverse events and protocol deviations will be recorded.
 
POD Day 35 (+/- 3 days) Telephone Contact by Study Team Post- (No Visit Required)
Study Medication is expected to be completed at this time. A Study Team member will contact each subject to confirm completion. Subjects will be asked to send to the Study Team, a copy of the Study Medication Log. All adverse events and protocol deviations will be recorded.
 
Visit 2: POD 3 Months (+/- 4 weeks)
Subjects will be asked to complete the following questionnaires either on paper or in electronic format.
 

• SF-12 – Short Form General Health Survey;

• Patient Satisfaction;

• Harris Hip Score (HHS);

• Vail Hip Score (VHS);

• Hip Outcome Score (HOS);

• Western Ontario and McMaster Universities Osteoarthritis Index (WOMAC);

• Tegner Activity Scale; and

• VAS Pain - Visual Analogue Scale for Pain.

 
Subjects will receive a focused physical exam, review of all medications, strength testing and range of motion (ROM) assessment. Adverse events related to the target hip and protocol deviations will be recorded.
 
POD 6 Months Post-operative -(No Visit Required) (+/- 4 week
 |
|--|---|

|                     |  |
|---------------------|--|

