At the conclusion of study medication, subjects will be contacted by the Study Team to confirm completion of medication. The occurrence protocol deviations and of all adverse events will be documented.

At three months post operatively, subjects will be seen for a visit The Steadman Clinic. A copy of the Medication Log will be retained by the Study Team, and subjects will complete Patient Reported Outcomes (PROs) either on paper or electronically. These tools are described in more detail in [Section 13.5](#) of this protocol. All medical history will be updated including all medications. Vital signs will be recorded, and subjects will undergo strength testing and range of motion assessment by the Principal Investigator or a designee. Protocol deviations and all adverse events related to the target hip will be collected.

At six and twelve months post operatively, subjects will be required to complete from home the assigned PROs electronically. Subjects will be contacted by phone and protocol deviations and all adverse events related to the target hip will be collected.

At eighteen months postoperatively, subjects will be seen at the Steadman Clinic. PRO questionnaires will be completed. Medical history will be updated including all medications. Vital signs will be recorded, and subjects will undergo strength testing and range of motion assessment by the Principal Investigator or a designee. In addition, morphological and quantitative T2 MRI will be performed to assess the regrowth of new cartilage tissue. protocol deviations and all adverse events related to the target hip will be collected.

After all subjects have reached 18 months follow-up, primary and secondary outcomes will be analyzed as described in [Section 17](#) of this document. Unblinding of the Study Team and the Subject will occur.

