**Printed Name of Person Obtaining Consent**

## 23.2 Appendix B – Study Schemata

|  | Standard of Care Used for Screening | Visit 1
POD 1    | Telephone Contact        | Telephone Contact
Day 35 | Visit 2
3 months | Telephone Contact       | Telephone Contact        | Visit 3
18 Months |
|--|-------------------------------------|---------------------|--------------------------|-----------------------------|---------------------|-------------------------|--------------------------|----------------------|
| Window   |                                     | (or upon discharge) | 7-10 days post discharge | +/- 3 days                  | +/- 4 weeks         | 6 months
+/- 4 weeks | 12 months
+/- 8 Weeks |                      |
| I/E Criteria   | X                                   |                     |                          |                             |                     |                         |                          |                      |
| Vitals, H&P  | X                                   |                     |                          |                             | X                   |                         |                          |                      |
| BMI  | X                                   |                     |                          |                             |                     |                         |                          |                      |
| Demographic Info   | X                                   |                     |                          |                             |                     |                         |                          |                      |
| Medical History  | X                                   |                     |                          |                             | X                   |                         |                          |                      |
| Trauma Chronology  | X                                   |                     |                          |                             |                     |                         |                          |                      |
| Circumduction eval   | X                                   |                     |                          |                             | X                   |                         |                          |                      |

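### Section 11.4 sets the last call for all adverse events at day 30, before the 12.2 window closes and against Day 35 elsewhere; and 12.5 leaves a hospitalisation that is not life-threatening outside the FDA report

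*Combined protocol and SAP*

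**What the plan says.** **Endpoint and window.** Section 9.4 lists the occurrence of adverse events (AEs) as a primary endpoint. Section 12.2 says: "Adverse events that occur up to 35 days +/- 3 days after the beginning Study Medication administration will be recorded". Section 11.2, headed for post-operative day 2, says: "Subjects begin taking Study Medication". The synopsis gives the window in another form: "All adverse events will be assessed during Study Medication administration and for 5 days (+/- 3) days after medication completion".

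**Last contact that collects all AEs.** The heading of 11.4 reads "Telephone Contact by Study Team Post-operative day 30- (No Visit Required" and adds that this is about one month; no tolerance is given. The synopsis has "POD Day 35 (+/- 3 days) Telephone Contact by Study Team Post- (No Visit Required" and Appendix B has "Telephone Contact Day 35", also with ± 3 days. Section 6.0 gives no date: "At the conclusion of study medication, subjects will be contacted by the Study Team to confirm completion of medication".

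**Next contact.** For Visit 2 at three months, 11.5 says: "Protocol deviations and adverse events related to the target hip will be recorded". The Appendix B footnote carries the same restriction. Section 12.2, in contrast, requires every required visit to record all AEs since the visit before it, and also to record AEs whenever they are reported.

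**Seriousness.** Section 12.5 lists two serious outcomes: death and a life-threatening event, the latter meaning immediate risk of death. Hospitalisation appears only in 12.3, inside severity Grade 4, beside disabling events. Section 12.6.1 sends serious and unexpected events to the unblinded Medical Monitor within 24 hours. It sends unanticipated and serious events to the IRB within 5 business days. It sends a serious and unexpected event on losartan to FDA by telephone or fax within 7 days, and in writing within 15.

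**The concern.** The dates and scopes that govern collection of a primary safety endpoint do not agree. Staff who follow 11.4 and 11.5 as written make their last enquiry about all AEs before the stated window ends, and then ask only about the operated hip. Staff who follow the synopsis and Appendix B come close to covering the window. What the AE table contains would then depend on which section was used.

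The definition of serious has a separate effect on expedited reporting. An event that puts a subject in hospital without immediate risk of death is recorded and tabulated, but it does not meet the 12.5 list on which the 12.6.1 reports depend.

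**Working it through.** **Part (a): day arithmetic**

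Inputs: first dose at POD 2 (11.2); window of 35 ± 3 days from the start of medication (12.2); medication plus 5 ± 3 days (synopsis); call at POD 30 (11.4) or Day 35 ± 3 (synopsis, Appendix B). The course is one month (section 6.0). The documents give no number of days, so I assume 28 to 31.

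1. *The plan's own figure.* A 30-day course plus 5 ± 3 days gives 35 ± 3 days. This reproduces 12.2, so the two window rules are essentially the same.

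2. *End of the 12.2 window.* With the first dose as day 0: 2 + 35 = POD 37 (34–40). With the first dose as day 1: POD 36 (33–39).

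3. *Gap after a POD 30 call, 12.2 rule.* 37 − 30 = 7 days (4–10), or 36 − 30 = 6 days (3–9). Together: nominally 6–7 days, range 3–10. As a share of the window, 6/35 = 17% and 7/35 = 20%.

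4. *Gap after a POD 30 call, synopsis rule.*

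| Month counted as | Last dose | Five post-medication days | Of these, after POD 30 | Gap at 5 days (2–8) |
|---|---|---|---|---|
| 28 days from POD 2 | POD 29 | POD 30–34 | 4 | 4 (1–7) |
| One month from surgery | POD 30 | POD 31–35 | 5 | 5 (2–8) |
| 30 days from POD 2 | POD 31 | POD 32–36 | 5 | 6 (3–9) |
| 31 days from POD 2 | POD 32 | POD 33–37 | 5 | 7 (4–10) |

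So 4 or 5 of the 5 nominal post-medication days follow the call, and the gap can be as short as 1–2 days.

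5. *A Day 35 call instead.* Counted from surgery, it is 36 − 35 = 1 to 37 − 35 = 2 days short of the nominal end. If made at its earliest, POD 32, it is 36 − 32 = 4 to 37 − 32 = 5 days short. Counted from the first dose, it is nominally 0 days short. Changing the date alone therefore does not close the gap; the origin of the count must also be stated.

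6. *Recall if Visit 2 does collect all AEs.* Take three months as 90 days, ± 28 (POD 62–118). Events on POD 31–37 are then asked about 90 − 37 = 53 to 90 − 31 = 59 days later. The extremes are 62 − 37 = 25 and 118 − 31 = 87 days.

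**Part (b): passages side by side**

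Take a Grade 4 disabling event with hospitalisation and no immediate risk of death. Under 12.5 it is not serious.

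- *FDA.* The trigger is worded in the singular, for one event that is both serious and unexpected. The event is outside it.
- *Medical Monitor.* If the phrase means both conditions, the event is outside. If it means serious events and also unexpected events, an unexpected hospitalisation is reported within 24 hours and an expected one is not.
- *IRB.* The 12.6.1 trigger has the same form, but 16.2 also requires AEs to be reported as the IRB demands. That route is partly covered.

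**The case against.** The date conflict may be a slip in one heading. Two of the three places that date the call say Day 35 ± 3, and 11.4 calls its own date approximate. Section 6.0 gives no date and so conflicts with neither. This explains the discrepancy but does not remove it, because 11.4 is the procedural section and has no tolerance that reaches Day 35.

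The backstop is real. The 12.2 window concerns when events occur, not when they are asked about, and the text on date of onset allows onset to differ from the date the team became aware. Both telephone contacts are headed as needing no visit, so at Visit 2 the previous visit is literally Visit 1, and the 12.2 sentence spans the whole window. Section 13.1 tells subjects to inform the investigator of losartan side effects. A reader might infer that late events are certainly lost; the documents do not support that. What stands is that 11.5 and Appendix B restrict the same visit to the target hip, and that spontaneous report or recall over weeks is weaker than a timed question.

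On part (b), severity and seriousness are separate scales, so the difference between 12.3 and 12.5 is not in itself a contradiction. A reader might also infer that such hospitalisations miss every report in 12.6.1. That goes too far. Section 12.5 itself uses an and/or form for serious and unexpected events, which favours the either/or reading. Section 12.4 defines expected events by the disease process, so a hospitalisation from a drug effect would normally count as unexpected and would reach the Monitor on that reading. Only the FDA route is firmly affected.

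**Conclusion.** The point holds as a reconciliation the sponsor should make, with medium confidence.

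(a) Under 11.4, the last scheduled enquiry about all AEs falls nominally 6–7 days before the 12.2 window ends, with the ranges shown above. The Day 35 date removes most of this gap but not all of it unless the day count shares an origin with the window. Visit 2 has two incompatible AE scopes.

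(b) A hospitalised or disabling event that is not life-threatening is outside the FDA report. It is outside the 24-hour Monitor report only if both conditions are required or the event is expected.

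The practical loss is probably small. The uncovered days fall mostly after dosing, and section 5.3 reports that adverse responses came early. The number of events affected is unknown. A reader might infer bias between arms, but both arms receive the same blinded call, and nothing in the documents supports that inference. The day counts rest on a first dose at POD 2, a month of 28 to 31 days, and three months taken as 90 days.

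**What to change.** (a) Reconcile 11.4, 11.5, 12.2, the synopsis and Appendix B under one stated day-count origin, so that the last contact collecting all AEs is not before the end of the stated window. Make the AE scope of Visit 2 in 11.5 and Appendix B agree with 12.2.

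(b) Reconcile 12.5 with 12.3 and 12.6.1 so that two things are each stated once: how hospitalised or disabling events are reported, and whether serious and unexpected means both or either. The sponsor decides the rule.

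The cost is protocol wording, a call about a week later than 11.4 states if the site has been following that section, and possibly slightly more safety reporting. No new procedures or patients are needed.

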### **Date of Onset and Resolution**

The date of onset is the time at which the subject reports that the incident began. This may or may not be the date on which the Study Team became aware of the event. The date of resolution is the date at which the event was no longer apparent to the subject and/or the Study Team. This may be unknown if at the end of the study the event is not resolved. In this case, the event will be indicated to be unresolved.

### **Incidence**

An AE may be classified as “intermittent” or “continuous if has no periods of abatement.

### **Relationship to Study Medication**

The Principal Investigator is required to assess whether there is a reasonable possibility that the Study Medication caused or contributed to an AE.

Many terms and scales are used to describe the degree of causality between a Study Medication and an event. The expression “reasonable causal relationship” is meant to convey in general that there are facts (evidence) or arguments to suggest a causal relationship (ICH E2A, III/A/1).

Determination of whether there is a reasonable possibility that a treatment caused or contributed to an AE includes assessing temporal relationships, biologic plausibility, association (or lack of association) with underlying disease, and presence (or absence) of a more likely cause.

As is recommended in FDA draft guidance document, Safety Reporting Requirements for INDs and BA/BE Studies (2010), we define four degrees of relatedness: “unrelated”, “probably not related”, “suspected adverse drug reaction” (SADR) or “adverse reaction”.

